10.4 Subgroup Analysis for Efficacy endpoints

Primary and secondary efficacy endpoints will be summarized in a similar way as discussed for main analysis approach for the following subgroups (within each subgroup category) based on the mITT Population. Subgroups will be interpreted with caution due to possible limited sample size within each subgroup category.

- Age group (7-11 years group, 12-17 years group)
- Race (white, non-white)
- Gender (male, female)

11 Safety Analyses

The safety analysis will be performed using the Safety Population. The safety parameters will include adverse events (AEs) and clinical laboratory parameters, vital sign (including postural), electrocardiographic (ECG) parameters, height, and weight. For each safety parameter of the clinical laboratory, vital signs, height, weight, and ECG parameters, the last non-missing safety assessment before the first dose of study intervention will be used as the baseline for all analyses of that safety parameter. Continuous variables will be summarized by number of participants and mean, SD, median, minimum, and maximum values. Categorical variables will be summarized by number and percentage of participants. The safety summaries will be provided by study intervention group.

11.1 Adverse Events

Adverse events will be coded by system organ class and preferred term using the *Medical Dictionary for Regulatory Activities*, version 23.0 or newer.

An AE will be considered a treatment-emergent adverse event (TEAE) if

- The AE began on or after the date of the first dose of study intervention; or
- The AE was present before the date of the first dose of study intervention, but increased in severity or became serious on or after the date of the first dose of study intervention

An AE that occurs more than 30 days after the last dose of study intervention will not be counted as a TEAE.

An AE will be considered a treatment-emergent serious adverse event (TESAE) if it is a TEAE that additionally meets any SAE criterion.

The number and percentage of participants reporting TEAEs in each study intervention group will be tabulated by descending percentage in any group, by system organ class and preferred term, and further categorized by severity and causal relationship to the study intervention. If more than 1 AE is coded to the same preferred term for the same participant, the participant will be counted only once for that preferred term using the greatest severity and strictest causality for the summarization by severity and causal relationship. The above summaries of TEAEs, further categorized by severity and causal relationship will also be provided within each age group. If there are 5 or less participants with severe or related TEAEs in any study intervention group, the

corresponding age group summaries for TEAEs by severity or causal relationship will not be provided.

The incidence of common ($\geq 5\%$ of participants in any study intervention group) TEAEs will be summarized by system organ class, preferred term, and study intervention group.

Summary tables will be provided for participants with TESAEs, AEs of special interest, and participants with AEs leading to discontinuation.

For all screened participants, separate listings will be presented for participants who died, participants with SAEs, participants with AEs leading to premature discontinuation, and participants with AEs of special interest (AESI). AEs during the Postintervention Period will also be included in the listings. A listing of all AEs will also be presented.

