### 2.2.2. Pediatric Linaclotide Program

A total of 214 pediatric participants were treated with linaclotide in two Phase 2 dose-ranging studies in the FC and IBS-C pediatric populations (LIN-MD-62 and LIN-MD-63, respectively).

LIN-MD-62 was a Phase 2 double-blind, placebo-controlled, parallel group, safety and efficacy study of a range of linaclotide doses administered to participants, 6 to 17 years of age, who fulfilled modified Rome III criteria for FC (refer to [Table 2-1](#) for dosing information). The objective of LIN-MD-62 was to evaluate the dose response, safety, and efficacy of 4 weeks of treatment with 1 of 3 linaclotide doses (Dose A, B, and C) or 145 µg (as an exploratory objective in the adolescent participants, 12 to 17 years of age, using the approved adult dose) compared with placebo in pediatric participants who fulfill modified Rome III criteria for child/adolescent FC with the goal of selecting an optimal dose of linaclotide to evaluate in this current confirmatory study.

A total of 173 participants were randomized to receive 1 of 3 proposed linaclotide doses (Dose A, B, and C) for pediatrics (n = 116 participants), the approved adult linaclotide dose (145 µg, n = 16 participants), or placebo (n = 41 participants) for 4 weeks of study intervention followed by a 1-week Postintervention Period ([Table 2-1](#)). For the primary and key secondary endpoints in the Phase 2 dose ranging LIN-MD-62 study, none of the 3 linaclotide doses (A [low dose], B [medium dose], and C [high dose]) indicated clear improvement over placebo (p-value  $\geq 0.1502$ ) based on analysis of the ITT population. However, a numerical trend toward efficacy at the higher doses was observed for the primary endpoint of change from baseline in 4-week overall SBM frequency rate (SBMs/week). Overall, linaclotide was well tolerated across all doses and both age groups. The safety profile was consistent with prior adult linaclotide studies for CIC. The most frequently reported TEAE was diarrhea, which occurred in 7.6% of linaclotide-treated participants versus 0% in the placebo group. The majority of the TEAEs of diarrhea reported were mild; none were severe. In the 12 to 17 years of age group, one participant experienced moderate diarrhea (related) leading to discontinuation in the linaclotide Dose C group.

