**Table 2-1 Dose Levels ( $\mu\text{g}$ ) by Weight in Pediatric Participants Treated with Linaclotide in LIN-MD-62**

Age Group (years)	Weight (kg)	Linaclotide Dose A ( $\mu\text{g}$ ) N = 36	Linaclotide Dose B ( $\mu\text{g}$ ) N = 41	Linaclotide Dose C ( $\mu\text{g}$ ) N = 39	Approved Adult Dose ( $\mu\text{g}$ ) N = 16
6–11	18 to <35	9	18	36	–
	$\geq 35$	18	36	72	–
12–17	N/A	18	36	72	145

LIN-MD-63 was a Phase 2, multicenter, randomized, double-blind, placebo-controlled, parallel-group, safety and efficacy dose-ranging study of linaclotide in children ages 7 to 17 years with IBS-C. The objectives of LIN-MD-63 were to evaluate the dose response, safety, and efficacy of 4 weeks of treatment with 1 of 3 linaclotide doses (Dose A, B, or C; refer to [Table 2-2](#) for dosing information) or 290  $\mu\text{g}$  (as an exploratory objective in the adolescent participants, 12 to 17 years of age, using the approved adult dose) compared with placebo in pediatric participants 7 to 17 years of age who fulfill the Rome III criteria for child/adolescent IBS and modified Rome III criteria for child/adolescent FC.

According to the original study design, approximately 260 participants with IBS-C were planned to be randomized in this study. However, due to slow participant enrollment, this study was terminated early based on FDA’s feedback (Type C Meeting for pediatric IBS-C, June 2019). The actual sample size achieved was 101 randomized participants, which is approximately 39% of the original planned sample size. These 101 IBS-C participants were randomized to receive 1 of 3 proposed linaclotide doses (Dose A, B, and C) for pediatrics (n = 74 participants), the approved adult linaclotide dose (290  $\mu\text{g}$ , n = 8 participants), or placebo (n = 19 participants) for 4 weeks of study intervention. For the primary efficacy endpoint of change from baseline in 4-week overall SBM frequency rate, numerical improvement was observed with each increasing linaclotide dose compared with placebo based on analysis of the ITT population. For the key secondary efficacy endpoint of change from baseline in 4-week abdominal pain daytime symptoms, numerical improvement was observed with linaclotide 290  $\mu\text{g}$  compared with placebo, while results were similar in the other linaclotide groups (Dose A, B, and C) compared with placebo.

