Overall, linaclotide was safe and well tolerated across all doses and both age groups. The safety profile was consistent with prior adult linaclotide studies for IBS-C. The most commonly reported TEAE was diarrhea. The majority of the TEAEs of diarrhea reported were mild; none were severe. In participants 12 to 17 years of age, AEs leading to discontinuation were reported in 1 participant in the linaclotide Dose B group (diarrhea [related]) and 1 participant in the placebo group (abdominal pain, anaphylactic reaction [SAE], and hematemesis; all considered not related to study treatment). There were no AESIs (ie, significant volume depletion and/or significant electrolyte abnormalities and/or ECG abnormalities that are considered by the investigator or sponsor to be related to diarrhea) or deaths reported. There were 2 SAEs reported

in participants 12-17 years of age (1 each in the placebo and linaclotide Dose A [36 µg] groups), neither of which were diarrhea, and neither were considered related to study intervention. Moreover, in pediatric participants 7 to 11 years of age, no SAEs or AEs leading to discontinuation were reported.

As with adults, linaclotide is minimally absorbed with low systemic availability in this pediatric population.

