**Table 2-2 Dose Levels (µg) by Weight in Pediatric IBS-C Participants Treated with Linaclotide in LIN-MD-63**

Age Group (years)	Weight (kg)	Linaclotide Dose A (µg) N = 29	Linaclotide Dose B (µg) N = 21	Linaclotide Dose C (µg) N = 24	Approved Adult Dose (µg) N = 8
7-11	18 to <35	18	36	72	-
	≥35	36	72	145	-
12-17	N/A	36	72	145	290

Additional information from studies conducted with linaclotide can be found in the linaclotide IB.

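### IBS-C SAP 11.1 can withhold the by-age TEAE severity or causality table for both doses because one dose arm had few cases: a minor reporting weakness, cheap to remove

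*SAP*

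**What the plan says.** IBS-C SAP 11.1 first makes a commitment: the TEAE summaries "further categorized by severity and causal relationship will also be provided within each age group". The next sentence withdraws it on a condition: "If there are 5 or less participants with severe or related TEAEs in any study intervention group". When that condition is met, the stated result is that "age group summaries for TEAEs by severity or causal relationship will not be provided". The IBS-C part has two groups, 145 µg and 290 µg. The sentence does not exempt an arm that has enough cases. It also does not say whether participants are counted over the whole arm or within each age group of an arm.

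IBS-C SAP 10.4 treats efficacy differently. Primary and secondary endpoints are summarized by age group with no count condition, only a warning: "Subgroups will be interpreted with caution due to possible limited sample size within each subgroup category".

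On prior exposure, Protocol 2.2.2 describes the 290 µg dose in LIN-MD-63 "as an exploratory objective in the adolescent participants, 12 to 17 years of age, using the approved adult dose". Protocol Table 2-2, which sets out the doses "by Weight in Pediatric IBS-C Participants Treated with Linaclotide in LIN-MD-63", shows 8 participants on 290 µg and a dash for that dose at ages 7 to 11. In LIN-MD-62 the highest dose was 145 µg, and only at ages 12 to 17 (Table 2-1).

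**The concern.** Neither Phase 2 pediatric study gave 290 µg at ages 7 to 11, and Protocol 4.3.2 acknowledges that younger children will now receive more per kilogram than in LIN-MD-63. Age group is also the only stratification factor. A table of severity and relatedness by age and dose is therefore the direct view of tolerability in the least-studied group, and the SAP planned it.

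The rule makes that table depend on the results, in an awkward direction. If the lower dose is well tolerated and the higher dose is not, the low count at 145 µg triggers the rule and the age breakdown at 290 µg goes with it. A reader would then have to rebuild the age-by-dose counts from listings. Sparse cells are a weak reason to withhold a display that is descriptive and carries no test.

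**Working it through.** The plan states no figure for how often the rule would apply, so there is nothing to reproduce. The check asks how often it would fire.

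**Inputs**
- Threshold: 5 or fewer in any arm (IBS-C SAP 11.1).
- Arm size: 50, the planned minimum (IBS-C SAP 14), so the threshold is 5/50 = 10% of an arm.
- Event rates: the documents give no related- or severe-TEAE rate for these doses in children. Diarrhea rates stand in for related TEAEs, which is an assumption. LIN-MD-62 reported diarrhea "which occurred in 7.6% of linaclotide-treated participants versus 0% in the placebo group" (Protocol 2.2.2). In adult IBS-C, MCP-103-302 had 79/402 = 19.7% and LIN-MD-31 had 79/406 = 19.5% (Protocol Table 10-3). LIN-MD-31 used 266 µg, which IBS-C SAP 10.1.1 counts with 290 µg.

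**Formula.** For each arm, F = P(X ≤ 5) with X ~ Binomial(50, p). With independent arms, P(dropped) = 1 − (1 − F₁)(1 − F₂).

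F(0.076) = 0.823; F(0.195) = 0.057; F(0.197) = 0.053.

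| Assumed rate, 145 µg v 290 µg | Calculation | P(dropped) |
|---|---|---|
| 19.7% v 19.7% | 1 − 0.947² | 0.10 |
| 19.5% v 19.5% | 1 − 0.943² | 0.11 |
| 7.6% v 19.7% | 1 − 0.177 × 0.947 | 0.83 |
| 7.6% v 7.6% | 1 − 0.177² | 0.97 |

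**One arm removing the other's table.** At 7.6% v 19.7%, the chance that the 290 µg arm has 6 or more cases but loses its age split because the 145 µg arm has 5 or fewer is F₁(1 − F₂) = 0.823 × 0.947 = 0.78.

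**Severity.** At 5% in both arms F = 0.962, so P(dropped) = 1 − 0.038² = 0.999. For context, the LIN-MD-63 account says of diarrhea: "The majority of the TEAEs of diarrhea reported were mild; none were severe". That study treated 29 + 21 + 24 + 8 = 82 participants with linaclotide. For 0 of 82 the one-sided 95% upper limit is 1 − 0.05^(1/82) = 3.6%. This covers severe diarrhea only; no rate is given for other severe events.

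**Other readings of the sentence**
- Count taken within age group, with 20 per arm (the 40% minimum of 50): even at 19.7% in both arms F = 0.814, so P(dropped) = 1 − 0.186² = 0.97.
- Table dropped only when every arm is at 5 or fewer: P = F₁F₂, which is 0.003 at 19.7% in both, 0.04 at 7.6% v 19.7%, 0.68 at 7.6% in both, and 0.93 at 5% in both.

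**The case against.** Most of the case on the other side concerns weight, and much of it stands.

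- **Nothing is lost.** All-ages severity and causality tables, summaries of serious events, special-interest events and discontinuations, and a listing of every AE are kept. The IBS-C part makes no dose comparison, so no inference is distorted.
- **The protocol does not require the table.** Protocol 9.2.5.2.1 only allows limited exploratory subgroup analyses. The SAP offers more and then limits the extra.
- **The proxy is imperfect.** The rule counts participants with any related TEAE, while diarrhea is one preferred term. Not all diarrhea is judged related, but on balance the figures probably overstate how often the causality table would be dropped. The 7.6% rate comes from a 4-week FC study at mostly lower doses. Fifty per arm is a minimum, and SAP 16.6 and 16.7 set missing severity to severe and missing causality to related for events starting on or after first dose. Both facts push counts up. The two adult IBS-C rates near 20% give only 10 to 11%.
- **Limiting sparse subgroups has precedent.** FC SAP 10.4 makes its efficacy subgroup analyses conditional on sample size.
- **The severity split adds least.** An arm that triggers the rule has at most 5 severe cases, each already in the all-ages table and the listings.

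What survives is narrow: as worded, one arm's low count can remove the other arm's age split, and the counting unit is open. None of the replies gives a reason for either.

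**Conclusion.** The point holds as a minor reporting weakness. On the most natural reading, few events at one dose remove the by-age severity or causality table for both. For causality the chance runs from about 10% to 97% over the rates shown, with 50 per arm, whole-arm counting, independent arms and a proxy that probably overstates it. For severity the table is very likely to go if severe TEAEs are at or below about 5%.

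A reader might infer that safety at ages 7 to 11 on 290 µg will go unreported, or that these children are less protected. The documents do not support either. The events are collected, listed and tabulated over all ages, and protection rests on the monitoring board, the mandatory discontinuation criteria and dose reduction, not on this table. A reader might also infer that the causality table is certain to disappear. That depends on a related-TEAE rate the documents do not give and on which reading of the sentence is applied.

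**What to change.** In IBS-C SAP 11.1, delete the count condition. Always show TEAEs by severity and by causality for each age group and dose arm as descriptive counts, carrying over the caution in SAP 10.4.

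At minimum, withhold a table only when every arm has 5 or fewer such participants, and state whether the count is over the arm or within age group. With whole-arm counting this cuts the chance of dropping the table at 7.6% v 19.7% from 83% to about 4%, but the severity table would still usually be absent at low rates (93% at 5% in both arms), so deletion is the better option.

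The cost is a few sparse tables. Data collection, dosing, eligibility, endpoints and sample size do not change. FC SAP 11.1 has the same sentence, and editing it is optional. The priority is low.

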11.2 Clinical Laboratory Parameters

Descriptive statistics for clinical laboratory values (in International System of Units [SI] units) and changes from the baseline values at each assessment time point will be presented by study intervention group for the following laboratory parameters:

Hematology: Absolute and differential white blood cell count, erythrocyte count, hemoglobin, hematocrit, platelet count, red blood cell count, and red blood cell indices (mean corpuscular volume, mean corpuscular hemoglobin, and mean corpuscular hemoglobin concentration)

Chemistry: Sodium, potassium, calcium, chloride, bicarbonate, magnesium, phosphate, glucose, blood urea nitrogen, creatinine, total protein, alkaline phosphatase (ALP), albumin, total bilirubin (TBL), alanine aminotransferase (ALT), aspartate aminotransferase (AST), total cholesterol

Urinalysis: Specific gravity and pH

Clinical laboratory test values will be considered potentially clinically significant (PCS) if they meet either the lower-limit or higher-limit PCS criteria listed in [Table 11-1](#). The number and percentage of participants who have PCS postbaseline clinical laboratory values will be tabulated by study intervention for the double-blind Intervention Period. The percentages will be calculated relative to the number of participants with available non-PCS baseline values and at least 1 postbaseline assessment for the double-blind Intervention Period. The numerator will be the total number of participants with available non-PCS baseline values and at least 1 PCS postbaseline value for the double-blind Intervention Period. A supportive tabular display of participants with PCS postbaseline values will be provided, including the PID number, baseline

and all postbaseline (including non-PCS) values. In this listing, any participant with PCS value (if any) during the Post-intervention period will also be included.

In addition, a tabular display showing all AEs that occurred in participants who had PCS postbaseline clinical laboratory values will be provided.

Shift tables from baseline to the end of double-blind Intervention Period for clinical laboratory parameters listed above will be presented by study intervention group for the following categories: low, normal, and high, which are provided by lab vendor.

Table 11-1. Criteria for Potentially Clinically Significant Laboratory Results

Parameter	SI Unit	Lower Limit	Higher Limit
CHEMISTRY			
Albumin	g/L	< 0.9 × LLN	> 1.1 × ULN
Alanine aminotransferase (ALT)	U/L	—	≥ 3 × ULN
Alkaline phosphatase	U/L	—	≥ 1.2 x ULN: 6-12 (inclusive), male & female; 13-15 (inclusive), male ≥ 3 × ULN: 13-15 (inclusive), female; 16- 17 (inclusive), male & female
Aspartate aminotransferase (AST)	U/L	—	≥ 3 × ULN
Bicarbonate	mmol/L	< 0.9 × LLN	> 1.1 × ULN
Bilirubin, total	µmol/L	—	> 1.5 × ULN
Calcium	mmol/L	< 0.9 × LLN	> 1.1 × ULN
Chloride	mmol/L	< 0.9 × LLN	> 1.1 × ULN
Cholesterol, Total	mmol/L	—	> 1.6 × ULN
Creatinine	µmol/L	—	> 1.3 × ULN
Glucose, random, serum	mmol/L	< 0.8 × LLN	> 1.4 × ULN
Potassium	mmol/L	< 0.9 × LLN	> 1.1 × ULN
Protein, total	g/L	< 0.9 × LLN	> 1.1 × ULN
Sodium	mmol/L	< 0.9 × LLN	> 1.1 × ULN
Urea Nitrogen (BUN)	mmol/L	—	> 1.2 × ULN
HEMATOLOGY			
Basophils, absolute cell count	10 ⁹ /L	—	> 3 × ULN
Eosinophils absolute cell count	10 ⁹ /L	—	> 3 × ULN
Lymphocytes absolute cell count	10 ⁹ /L	< 0.7 × LLN	> 1.3 × ULN
Monocytes, absolute cell count	10 ⁹ /L	< 0.5 × LLN	> 2.0 × ULN
Neutrophils, absolute cell count	10 ⁹ /L	< 0.8 × LLN	> 1.5 × ULN
Hematocrit	Ratio	< 0.9 × LLN	> 1.1 × ULN
Hemoglobin	g/L	< 0.9 × LLN	> 1.1 × ULN
Platelet count	10 ⁹ /L	< 0.5 × LLN	> 1.5 × ULN
Red blood cell count	10 ¹² /L	< 0.9 × LLN	> 1.1 × ULN
White blood cell count	10 ⁹ /L	< 0.7 × LLN	> 1.5 × ULN
URINALYSIS			
pH	—	< 0.9 × LLN	> 1.1 × ULN
Specific gravity	—	—	> 1.1 × ULN

LLN = lower limit of normal value provided by the laboratory; SI = *Le Système International d'Unités* (International System of Units); ULN = upper limit of normal value provided by the laboratory.

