#### **9.1.5.2.2. Clinical Laboratory Assessments**

Descriptive statistics for clinical laboratory values (in SI units) at baseline (screening) and changes from baseline at each assessment time point will be presented by study intervention group.

The criteria for potentially clinically significant (PCS) laboratory values will be detailed in the SAP. The number and percentage of participants who have PCS postbaseline clinical laboratory values will be tabulated by study intervention during the double-blind study intervention period. The percentages will be calculated relative to the number of participants who have available non-PCS baseline values and at least 1 postbaseline assessment for the double-blind study intervention period. The numerator will be the total number of participants with available non-PCS baseline values and at least 1 PCS postbaseline value during the double-blind study intervention period. A supportive listing of participants with PCS postbaseline values will be provided for the Safety Population.

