Other laboratory assessments may be repeated at any visit if there was an abnormal finding at the most recent previous evaluation or if additional information is clinically necessary to appropriately evaluate the participant's current condition, follow up, and/or manage an adverse experience.

A central laboratory will be used to evaluate all urine (except urine pregnancy tests) and blood samples, which will be collected, processed, and stored according to the instructions provided by the laboratory. The urine pregnancy test at Visits 3, 5 to 7 will be completed at the study site.

Protocol-specific requirements for inclusion or exclusion of participants are detailed in Section 5 of the protocol.

Additional tests may be performed at any time during the study as determined necessary by the investigator or required by local regulations.

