16.1 Visit Time Windows for Safety Analyses

Table 16-1 presents the visits assigned for safety analyses and the corresponding range of study intervention days (window) during which an actual visit may occur.

Table 16-1. Visit Time Windows

Derived Visit	Scheduled Visit Day^a	Window
Baseline	Day 1	Days ≤ 1
Week 2 Visit	Day 15	Days [2, 21]
Week 4 Visit	Day 29	Days [22, 42]
Week 8 Visit	Day 57	Days [43, 70]
Week 12 Visit	Day 85	Days [Day 71, max (last dose day+1, Visit 7 date)]
Post-intervention Visit	Day 92	Days \geq max (last dose day+1, Visit 7 date)+1
End of Double-Blind Intervention Period ^b	Final or Termination Visit during the double-blind Intervention Period	

- Relative to the date of the first dose of double blind study intervention. Day 1 = the date of the first dose of double blind study intervention. There is no Day 0 or Week 0.
- Presented in analysis tables for safety parameters, including but not limited to electrocardiograms, clinical laboratory values, and vital signs.

Participants who rollover to the long-term safety study, LIN-MD-66, before the EOS visit (i.e. Visit 8, post-intervention visit) are not required to have this EOS visit or post-intervention visit.

If the assessment date (if the assessment date is unavailable, use visit date instead) is on or after the date of the first dose of study intervention, the study day is calculated by assessment date - date of the first dose of study intervention + 1. If the assessment date is before the date of the first dose of study intervention, the study day is calculated by assessment date - date of the first dose of study intervention. Therefore, a negative day indicates a day before the start of the study intervention.

If a participant has 2 or more visits within the same window, the last visit with a non-missing value will be used for analysis.

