16.4 Repeated or Unscheduled Assessments of Safety Parameters

If a participant has repeated assessments before the start of the first study intervention, the results from the final non-missing assessment made prior to the start of the study intervention will be used as baseline. If end-of-study assessments are repeated or if unscheduled visits occur, the last non-missing postbaseline assessment will be used as the end-of-study assessment for generating summary statistics. However, all postbaseline assessments will be used for PCS value determinations, and all assessments will be presented in the data listings.

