Albumin	g/L	$< 0.9 \times \text{LLN}$	$> 1.1 \times \text{ULN}$
Alanine aminotransferase (ALT)	U/L	—	$\geq 3 \times \text{ULN}$
Alkaline phosphatase	U/L	—	$\geq 1.2 \times \text{ULN}$: 6-12 (inclusive), male & female; 13-15 (inclusive), male $\geq 3 \times \text{ULN}$: 13-15 (inclusive), female; 16- 17 (inclusive), male & female
Aspartate aminotransferase (AST)	U/L	—	$\geq 3 \times \text{ULN}$
Bicarbonate	mmol/L	$< 0.9 \times \text{LLN}$	$> 1.1 \times \text{ULN}$
Bilirubin, total	$\mu\text{mol/L}$	—	$> 1.5 \times \text{ULN}$
Calcium	mmol/L	$< 0.9 \times \text{LLN}$	$> 1.1 \times \text{ULN}$
Chloride	mmol/L	$< 0.9 \times \text{LLN}$	$> 1.1 \times \text{ULN}$
Cholesterol, Total	mmol/L	—	$> 1.6 \times \text{ULN}$
Creatinine	$\mu\text{mol/L}$	—	$> 1.3 \times \text{ULN}$
Glucose, random, serum	mmol/L	$< 0.8 \times \text{LLN}$	$> 1.4 \times \text{ULN}$
Potassium	mmol/L	$< 0.9 \times \text{LLN}$	$> 1.1 \times \text{ULN}$
Protein, total	g/L	$< 0.9 \times \text{LLN}$	$> 1.1 \times \text{ULN}$
Sodium	mmol/L	$< 0.9 \times \text{LLN}$	$> 1.1 \times \text{ULN}$
Urea Nitrogen (BUN)	mmol/L	—	$> 1.2 \times \text{ULN}$
HEMATOLOGY			
Basophils, absolute cell count	$10^9/\text{L}$	—	$> 3 \times \text{ULN}$
Eosinophils absolute cell count	$10^9/\text{L}$	—	$> 3 \times \text{ULN}$
Lymphocytes absolute cell count	$10^9/\text{L}$	$< 0.7 \times \text{LLN}$	$> 1.3 \times \text{ULN}$
Monocytes, absolute cell count	$10^9/\text{L}$	$< 0.5 \times \text{LLN}$	$> 2.0 \times \text{ULN}$
Neutrophils, absolute cell count	$10^9/\text{L}$	$< 0.8 \times \text{LLN}$	$> 1.5 \times \text{ULN}$
Hematocrit	Ratio	$< 0.9 \times \text{LLN}$	$> 1.1 \times \text{ULN}$
Hemoglobin	g/L	$< 0.9 \times \text{LLN}$	$> 1.1 \times \text{ULN}$
Platelet count	$10^9/\text{L}$	$< 0.5 \times \text{LLN}$	$> 1.5 \times \text{ULN}$
Red blood cell count	$10^{12}/\text{L}$	$< 0.9 \times \text{LLN}$	$> 1.1 \times \text{ULN}$
White blood cell count	$10^9/\text{L}$	$< 0.7 \times \text{LLN}$	$> 1.5 \times \text{ULN}$
URINALYSIS			
pH	—	$< 0.9 \times \text{LLN}$	$> 1.1 \times \text{ULN}$
Specific gravity	—	—	$> 1.1 \times \text{ULN}$

LLN = lower limit of normal value provided by the laboratory; SI = *Le Système International d'Unités* (International System of Units); ULN = upper limit of normal value provided by the laboratory.

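### In both SAPs the only PCS criterion for urine specific gravity, above 1.1 × ULN, sets a cut-off of at least 1.100 for any ULN of 1.000 or more; if no urine value exceeds 1.100, it can flag nobody

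*SAP*

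**What the plan says.** The protocol does not set the limits itself. Section 9.1.5.2.2 says: "The criteria for potentially clinically significant (PCS) laboratory values will be detailed in the SAP". Section 9.2.5.2 has the IBS-C safety analyses follow the FC approach.

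In each SAP, Section 11.2 makes a laboratory value PCS only if it meets a lower or higher limit in Table 11-1. The specific gravity row in the IBS-C SAP reads "Specific gravity — — > 1.1 × ULN": no lower limit, and one multiplicative upper limit. The FC SAP's Table 11-1 has the same row. The footnote to each table says that the ULN comes from the laboratory, and no numerical ULN is given.

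Section 11.2 of each SAP then plans three outputs from these limits: a count and percentage of participants with a postbaseline PCS value by study intervention, a supporting display of those participants, and a display of all AEs in participants with PCS values.

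Specific gravity is also reported in other ways. Section 11.2 of each SAP plans descriptive statistics and, in the words of the IBS-C SAP, "Shift tables from baseline to the end of double-blind Intervention Period for clinical laboratory parameters listed above will be presented by study intervention group", using the vendor's low, normal and high categories. Under Section 16.4, "all postbaseline assessments will be used for PCS value determinations, and all assessments will be presented in the data listings".

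**The concern.** A multiplier of 1.1 is a sensible way to step outside the normal range for an analyte measured from zero, such as sodium or calcium. Specific gravity is different. It is the density of urine relative to water, so pure water scores 1.000 and the information lies in the small excess above that. A 10% increase applied to the whole ratio adds at least 0.100, which is several times the excess that an ordinary upper limit would allow.

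If the limit lies beyond anything urine can show, the PCS count for this parameter is settled before any data are collected. It would be 0 in every group, and the criterion could put no participant into the PCS display or the AE display. A reader of the report could take such a zero as an observation about linaclotide, when it would only reflect the rule.

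**Working it through.** **Inputs from the documents.** The criterion is strictly greater than 1.1 × ULN, with no lower limit (Table 11-1, both SAPs). There is no other route to a PCS flag (Section 11.2, both SAPs). The SAPs state no expected count for this row, so there is no plan figure to reproduce.

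**Inputs not in the documents, taken as assumptions.** The laboratory's ULN is at least 1.000, illustrated by 1.025 to 1.035. The highest value urine can show is varied below.

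**Step 1: the cut-off, 1.1 × ULN, and how far it lies above water.** The last column is (cut-off − 1) / (ULN − 1).

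| Assumed ULN | Cut-off | Excess of cut-off ÷ excess of ULN |
|---|---|---|
| 1.000 | 1.100 | not defined |
| 1.025 | 1.1275 | 0.1275 / 0.025 = 5.1 |
| 1.030 | 1.133 | 0.133 / 0.030 = 4.4 |
| 1.035 | 1.1385 | 0.1385 / 0.035 = 4.0 |

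The cut-off rises with the ULN, so it is at least 1.100 for every ULN of 1.000 or more. Because the inequality is strict, a value of 1.100 or less is never flagged.

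**Step 2: the inverse.** A highest value m can be flagged only if ULN < m / 1.1.

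| Assumed highest value m | Flag reachable only if ULN is below |
|---|---|
| 1.04 | 0.945 |
| 1.05 | 0.955 |
| 1.06 | 0.964 |
| 1.10 | 1.000 |
| 1.12 | 1.018 |
| 1.15 | 1.045 |

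For a highest value of 1.04 to 1.06 the ULN would have to be below that of water. The last two rows show the other side: if urine values of 1.12 or 1.15 could occur, some ULNs above 1.000 would allow a flag.

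**Step 3: what is lost if nothing can be flagged.** The PCS determination uses every postbaseline value. By-visit tables do not. Under Section 16.1, "If a participant has 2 or more visits within the same window, the last visit with a non-missing value will be used for analysis". Under Section 16.4, "the last non-missing postbaseline assessment will be used as the end-of-study assessment for generating summary statistics", and that value may come from an unscheduled visit. The only information that the PCS count could add to the other tables is therefore mainly a by-group count that includes high values later superseded. These would be few. The protocol's Schedule of Activities has one postbaseline laboratory draw, at Week 12/EOT, so superseded values come only from repeat or unscheduled draws, which Appendix 2 allows: "Other laboratory assessments may be repeated at any visit if there was an abnormal finding at the most recent previous evaluation".

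**The case against.** The strongest reply is that only the cut-off is proven from the documents. The zero count needs two outside premises, a ULN of at least 1.000 and no urine value above 1.100. That is right, and the conclusion is conditional on both.

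Three stronger readings are tempting and are not supported:

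- **That the count is zero whatever the data.** It is zero only under the assumption on the highest urine value. A recorded value of 1.150 would be flagged for any ULN below about 1.045.
- **That the report will print a row of 0 of n with known denominators.** Both SAPs keep the table specifications in a separate document, so whether a zero row appears is unknown. The planned arm sizes do not cap n either. Section 6.4 of each SAP groups participants by the intervention received for most of the period. In the IBS-C part this includes participants who were dose-reduced under protocol Section 6.6, so a safety group can be larger than its randomized arm.
- **That high specific gravity, or dehydration, would go unseen.** It would not. Descriptive statistics, vendor shift tables and full listings remain. Investigators must review laboratory reports and record clinically relevant changes as AEs (protocol Section 8.2.4). Significant volume depletion judged related to diarrhea is an AESI (Section 8.3.1). PCS limits also exist for urea nitrogen, creatinine, sodium and postural vital signs.

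It can also be said that above ULN is a weak PCS limit, since no other row of Table 11-1 uses a bare ULN. That stands, and it is a reason to prefer deleting the row.

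**Conclusion.** The concern holds as a minor one. In both SAPs the single PCS criterion for specific gravity is scaled to the wrong quantity, and its cut-off is at least 1.100 for any ULN of 1.000 or more. Assuming that no urine value exceeds 1.100, and barring data errors, no value can meet it. The specific gravity PCS count is then 0 in every safety group of both parts of the study, and the criterion can add nobody to the PCS display or to the AE display.

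The cut-off arithmetic is certain. The zero count is as secure as the assumption on the highest urine value, which the laboratory can confirm from its reportable range. The practical loss is very small, because every other display of specific gravity is intact. No efficacy result, error rate, stopping rule or AESI determination depends on this row.

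**What to change.** Before unblinding, remove the specific gravity row from Table 11-1 in both SAPs and rely on the vendor's low/normal/high shift table. Under the stated assumption this gives up no information, and it prevents a predetermined 0% from being read as a safety finding.

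If the sponsor wants a PCS count for this parameter, replace the criterion with one that the laboratory's reportable range can reach. An example is above ULN, footnoted as a reporting flag only. Its cost is some mild flags in all groups, overlap with the vendor's high category, and a smaller denominator, because participants already above ULN at baseline drop out of it.

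Either change is one table row, with a footnote at most, in each SAP. If unblinding has already taken place, a footnote stating that the criterion is not expected to be reachable would still prevent misreading.
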